6.9 Duration of Therapy

Subjects enrolled after Amendment 7 (version date 08NOV2021) will remain on study treatment for up to 12 months. After consultation with PI, subjects enrolled prior to Amendment 7 (version date 08NOV2021) who have demonstrated a response to study treatment may continue beyond 12 months of treatment, if there is demonstrated continued clinical benefit.

Study treatment may continue beyond initial radiographic or clinical disease progression for up to 12 months as long as the patient is deriving clinical benefit from the treatment, as assessed by the investigator.

Subjects must be withdrawn from the study treatment for the following reasons:

- Subject withdraws consent from the study treatment and/or study procedures. A subject must be removed from the trial at his/her own request or at the request of his/her legally acceptable representative. At any time during the trial and without giving reasons, a subject may decline to participate further. The subject will not suffer any disadvantage as a result.
- Radiographic disease progression by RECIST v1.1 (progression must be confirmed with follow up scan no less than 4 weeks and no more than 8 weeks after the first scan shows disease progression). Study treatment may continue beyond initial radiographic disease progression as long as the patient is deriving clinical benefit from the treatment, as assessed by the investigator.
- Progressive disease (PD), without clinical benefit, as determined by the investigator.
- Specific conditions described in the Management of Adverse Events Section 7.
- An AE or intercurrent illness that in the opinion of the investigator warrants the subject's withdrawal from study treatment.
- Subject is lost to follow-up.
- Necessity for treatment with other treatment prohibited by protocol.
- Sexually active subjects who refuse to use medically accepted barrier methods of contraception (e.g., male condom, female condom) during the course of the study and for 120 days after discontinuation of study treatment.
- Women who become pregnant or are breastfeeding.
- If the subject does not recover from his or her toxicities to tolerable Grade ≤ 2 within 6 weeks, the subject will have study treatment discontinued unless there is unequivocal evidence that the subject is benefitting. In this situation, a subject may be able to restart therapy with a dose reduction upon resolution of the toxicity.
- Request by regulatory agencies for termination of treatment of an individual subject or all subjects under the protocol.
- Significant noncompliance with the protocol schedule in the opinion of the investigator.

- The starting dose of Cabozantinib study treatment will be 40 mg once daily (qd), (with dose reduction allowed for documented adverse events to 20 mg daily, and then to 20 mg every other day to improve tolerability.)

Subjects may be withdrawn from the study for the following reasons:

- The subject is non-compliant with study drug, trial procedures, or both; including the use of anti-cancer therapy not prescribed by the study protocol.
- If, in the investigator's opinion, continuation of the trial would be harmful to the subject's well-being.
- Development of an intercurrent illness or situation which would, in the judgment of the investigator, significantly affect assessments of clinical status and trial endpoints.
- Deterioration of ECOG performance status to 4.

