7.3 Contraception

Pembrolizumab may have adverse effects on a fetus in utero. Furthermore, it is not known if pembrolizumab has transient adverse effects on the composition of sperm.

For this trial, male subjects will be considered to be of non-reproductive potential if they have azoospermia (whether due to having had a vasectomy or due to an underlying medical condition).

Female subjects will be considered of non-reproductive potential if they are either:

(1) postmenopausal (defined as at least 12 months with no menses without an alternative medical cause; in women < 45 years of age a high follicle stimulating hormone (FSH) level in the postmenopausal range may be used to confirm a post-menopausal state in women not using hormonal contraception or hormonal replacement therapy. In the absence of 12 months of amenorrhea, a single FSH measurement is insufficient.);

OR

(2) have had a hysterectomy and/or bilateral oophorectomy, bilateral salpingectomy or bilateral tubal ligation/occlusion, at least 6 weeks prior to screening;

OR

(3) has a congenital or acquired condition that prevents childbearing.

Female and male subjects of reproductive potential must agree to avoid becoming pregnant or impregnating a partner, respectively, while receiving study drug and for 120 days after the last dose of study drug by complying with one of the following:

(1) practice abstinence[†] from heterosexual activity;

OR

(2) use (or have their partner use) acceptable contraception during heterosexual activity.

Acceptable methods of contraception are[‡]:

Single method (one of the following is acceptable):

- Intrauterine device (IUD)

- Vasectomy of a female subject's male partner
- Contraceptive rod implanted into the skin

Combination method (requires use of two of the following):

- Diaphragm with spermicide (cannot be used in conjunction with cervical cap/spermicide)
- Cervical cap with spermicide (nulliparous women only)
- Contraceptive sponge (nulliparous women only)
- Male condom or female condom (cannot be used together)
- Hormonal contraceptive: oral contraceptive pill (estrogen/progestin pill or progestin-only pill), contraceptive skin patch, vaginal contraceptive ring, or subcutaneous contraceptive injection

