†Abstinence (relative to heterosexual activity) can be used as the sole method of contraception if it is consistently employed as the subject's preferred and usual lifestyle and if considered acceptable by local regulatory agencies and ERCs/IRBs. Periodic abstinence (e.g., calendar, ovulation, sympto-thermal, post-ovulation methods, etc.) and withdrawal are not acceptable methods of contraception.

‡If a contraceptive method listed above is restricted by local regulations/guidelines, then it does not qualify as an acceptable method of contraception for subjects participating at sites in this country/region.

Subjects should be informed that taking the study medication may involve unknown risks to the fetus (unborn baby) if pregnancy were to occur during the study. In order to participate in the study subjects of childbearing potential must adhere to the contraception requirement (described above) from the day of study medication initiation (or 14 days prior to the initiation of study medication for oral contraception) throughout the study period up to 120 days after the last dose of trial therapy. If there is any question that a subject of childbearing potential will not reliably comply with the requirements for contraception, that subject should not be entered into the study.

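### Read literally, the contraception stop in Section 6.9 withdraws subjects who fully comply with Section 7.3, both single-method users and subjects of non-reproductive potential

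*Combined protocol and SAP*

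**What the plan says.** Section 6.9 has two withdrawal lists, one mandatory and one discretionary. The mandatory list opens with "Subjects must be withdrawn from the study treatment for the following reasons", and one of its bullets is "Sexually active subjects who refuse to use medically accepted barrier methods of contraception (e.g., male condom, female condom"), applied during the study and for 120 days after treatment stops. The bullet does not mention Section 7.3, gives the investigator no discretion, and makes no exception for other methods or for people who cannot conceive or father a child.

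Section 7.3 sets the contraception standard. It first defines who is of non-reproductive potential: azoospermic men, and women who are postmenopausal, surgically sterile by the listed procedures, or unable to bear children because of a congenital or acquired condition. Everyone else must practise abstinence or use acceptable contraception until 120 days after the last dose. Acceptable contraception takes two forms:

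- "Single method (one of the following is acceptable"): an IUD, vasectomy of a female subject's male partner, or "Contraceptive rod implanted into the skin".
- "Combination method (requires use of two of the following"): diaphragm, cervical cap, sponge, condom or hormonal contraceptive. The condom entry reads "Male condom or female condom (cannot be used together").

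Section 7.3 then makes adherence a condition of participation: "In order to participate in the study subjects of childbearing potential must adhere to the contraception requirement (described above").

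Inclusion criterion 5.2.11 refers to Section 7.3 and applies only where there is a risk of conception.

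**The concern.** The entry rule and the stopping rule use different tests. A subject can be enrolled under 5.2.11, follow 7.3 throughout, and still meet a mandatory reason for withdrawal under 6.9. A site that applies 6.9 as written would stop study treatment, while a site that applies 7.3 would continue. Section 4.3 allows up to three centres, so similar subjects could be handled differently.

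At stake are fair and consistent handling of participants and, for an affected subject, loss of protocol treatment for a reason that the contraception section does not support. There is also a lesser gap the other way: the mandatory stop does not reach a subject whose contraception 7.3 regards as inadequate.

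**Working it through.** There is no planned figure to reproduce. The check applies each rule to each kind of subject.

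**Inputs.** The 6.9 trigger is: sexually active, and refuses barrier methods. The 7.3 duty is: if of reproductive potential, then abstinence, one listed single method, or two listed combination methods.

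| Subject | Section 7.3 | Section 6.9 bullet | Result |
|---|---|---|---|
| Reproductive potential; IUD, partner vasectomy or implant only; declines condoms | Complies | Triggered | Conflict |
| Non-reproductive potential, sexually active; declines condoms | Nothing required | Triggered | Conflict |
| Reproductive potential; a permitted two-method combination | Complies | Not triggered | Agree |
| Abstinent | Complies | Not triggered | Agree |
| Reproductive potential; refuses every method | Does not comply | Triggered | Agree |
| Reproductive potential; condom alone, declines a second method | Does not comply | Not triggered | Gap |

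**Why two-method users do not conflict.** The combination list has five items, which gives C(5,2) = 10 pairs. One pair is barred, as the diaphragm entry shows: "Diaphragm with spermicide (cannot be used in conjunction with cervical cap/spermicide"). That leaves 10 − 1 = 9. Only the hormonal item is not a barrier, so no pair can lack one, and all 9 contain a barrier.

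This assumes that the diaphragm, cap and sponge count as barriers, because 6.9 names condoms only as examples. If a site counted condoms alone, 4 of the 9 pairs would contain one (a condom with each of the other four items). The other 9 − 4 = 5 pairs would then conflict too.

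**The condom-only subject.** Three provisions remain for this subject:

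- The participation condition in 7.3, which names no on-treatment action.
- The discretionary item in 6.9 on non-compliance with drug or procedures.
- The mandatory item in 6.9 on significant noncompliance, which is worded around the protocol schedule and left to the investigator's opinion.

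None clearly mandates a stop, and none permits the subject to continue.

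**Reconciling text.** No section ranks 6.9 against 7.3, and none says that a barrier must be added to a single method.

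**The case against.** The strongest reply is that 6.9 should be read in the light of 7.3: its author meant refusal of required contraception, and no sensible investigator would stop treatment in a postmenopausal woman over condoms. That is probably the intent. But the bullet sits under a mandatory heading without discretion, whereas other bullets in the same list defer to the investigator. A site following common sense would be departing from the written rule.

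Three further points have some force:

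- **The conflict needs a refusal that someone hears about.** The Section 8 calendar has no contraception check, only pregnancy tests. This limits how often the bullet would operate but does not make it correct.
- **A subject can satisfy both rules by adding a condom.** This is true, but 7.3 says that one method is enough and no section states a cumulative duty.
- **The condom-only case is not a contradiction.** This stands. Section 6.9 is silent there, so it is a gap in the mandatory trigger, not two opposing orders.

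A reader might infer that 6.9 ends all first-line cancer therapy for an affected subject. The documents do not support that. The bullet ends study treatment. Pembrolizumab is supplied as standard of care (6.3.1) at the approved dose and schedule (3.2.3), and nothing shows that it must stop off study. The loss the documents establish is protocol treatment, including the supplied cabozantinib.

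**Conclusion.** The point holds as an inconsistency in an operative stopping rule. Read literally, Section 6.9 requires withdrawal of two groups who comply with Section 7.3: users of the three single non-barrier methods who decline condoms, and sexually active subjects of non-reproductive potential who decline them. It is tempting to confine the conflict to the three single methods and express it as a share of the listed options. That would misstate the scope, because 6.9 also reaches people of whom 7.3 asks nothing, and options on a list are not subjects. The condom-only gap is real but secondary.

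The documents do not give the number of subjects affected, and it is probably small. A reader might also infer harm to the primary analysis, but none is claimed. Section 9.4 schedules an end-of-treatment CT for patients who stop for reasons other than progression, and no sample size or precision figure depends on this rule.

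The conclusion rests on reading 6.9 as written, on taking sexual activity to mean heterosexual activity as in 7.3, and on counting the diaphragm, cap and sponge as barriers. The correction should be made, because a mandatory rule gives the wrong result as worded and the remedy costs almost nothing.

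**What to change.** Replace the Section 6.9 bullet with:

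*Subjects of reproductive potential who refuse to comply with the contraception requirement in Section 7.3 (abstinence or an acceptable method, during study treatment and for 120 days after the last dose).*

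This makes 7.3 the single standard. It removes both conflicts and brings within the trigger a condom-only subject who refuses a second method. Refusal remains the test, so an isolated lapse does not force a stop. The 120-day period is kept so that a subject who, while on treatment, refuses the post-treatment duty still meets the trigger.

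The cost is one bullet in the next amendment, with the sponsor-side and IRB approvals that Section 15.8 already requires. There are no new visits, procedures or data, and no change to the analysis.

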7 TOXICITIES AND DOSEAGE MODIFICATION

This study will utilize the CTCAE (NCI Common Terminology Criteria for Adverse Events) Version 5.0 for adverse event and serious adverse event reporting.

7.1 Dose Modifications and Guidelines for Adverse Event Management for Cabozantinib

Subjects will be monitored for AEs from the start of treatment through 30 days after the date of the last dose of cabozantinib treatment. Subjects will be instructed to notify their physician immediately at the onset of any AE. Causality assessment of AEs will be determined by the investigator. AE severity will be graded by the investigator in accordance with CTCAE v.5.0. The following should be taken into consideration in decisions regarding dose modifications (reductions or interruption):

- As a general approach, all AEs should be managed with supportive care at the earliest signs of toxicity considered related to the study treatment. Should this be ineffective, dose interruptions and/or reductions should be considered to prevent worsening of toxicity.
- The assigned starting dose for cabozantinib is 40 mg/day. Dose reductions are permitted per PI discretion (see Table 7.1). Dose re-escalation level (See 7.2) of cabozantinib is permitted.
- Dose interruptions and/or reductions should be implemented for unacceptable toxicity. Doses may be modified at any time while on study.
- Interruption of cabozantinib treatment for AEs may occur at any time per investigator discretion. If treatment is interrupted due to AEs for more than 6 weeks, all study treatment should be discontinued unless there is unequivocal evidence that the subject is benefitting. In this situation, a subject may be able to restart therapy with a dose reduction upon resolution of the toxicity.

- Dose interruptions for reason(s) other than related AEs (e.g., surgical procedures) can be longer than 6 weeks per the discretion of the investigator.

Table 7.1

Assigned dose	Dose Level Reduction
40-mg cabozantinib oral, qd	20-mg cabozantinib oral, qd.
20-mg cabozantinib oral, qd	20-mg cabozantinib oral, qad

Table 7.2

Assigned dose	Dose Level Escalation
20-mg cabozantinib, oral qad	20-mg cabozantinib, oral qd
20-mg cabozantinib, oral qd	40-mg cabozantinib, oral qd

Table 7.3: Dose Modifications of Cabozantinib for Treatment-Related AEs

CTCAE v.5.0 Grade	Recommended Guidelines for Management ^a
Grade 1 AEs	Add supportive care as indicated. Continue cabozantinib treatment at the current dose level if AE is manageable and tolerable.
Grade 2 AEs that are tolerable and are easily managed	Continue cabozantinib treatment at the current dose level with supportive care.
Grade 2 AEs that are intolerable and cannot be adequately managed	At the discretion of the investigator, cabozantinib should be dose reduced or interrupted. Note: It is recommended that dose holds be as brief as possible.
Grade 3 AEs (except clinically non-relevant laboratory abnormalities)	Cabozantinib should be interrupted unless the toxicity can be easily managed with a dose reduction and optimal medical care. Note: It is recommended that dose holds be as brief as possible.
Grade 4 AEs (except clinically non-relevant laboratory abnormalities)	Subjects should have cabozantinib interrupted immediately. Permanently discontinue all study treatment unless the following criteria are met: 
• Subject is deriving clear clinical benefit as determined by the investigator• Toxicity can be managed with a dose reduction following recovery to Grade 1 (or baseline) and optimal medical care

Note: The dose delay and modification criteria for specific medical conditions are provided in Section 7.1.1. For re-treatment criteria of study treatment after a dose hold see Section 7.1.1.

^a Study treatment dose adjustment is only needed if the toxicity was deemed related to cabozantinib treatment or had an unclear relationship to cabozantinib treatment.

7.1.1 Guidelines for Management of Potential Adverse Events for Cabozantinib

Management of severe or intolerable adverse reactions may require temporary dose reduction and/or interruption for cabozantinib.

All study treatment should be permanently discontinued for the following AEs: visceral perforation or fistula formation, severe hemorrhage, serious arterial thromboembolic events,

nephrotic syndrome, hypertensive emergency, persistent uncontrolled hypertension despite optimal medical management, and reversible posterior leukoencephalopathy syndrome (RPLS).

Gastrointestinal perforation, GI fistula, and intra-abdominal and pelvic abscess: After starting treatment with cabozantinib, subjects should be monitored for early signs of GI perforation such as abdominal pain, nausea, emesis, constipation, and fever especially if known risk factors for developing GI perforation or fistula are present.

Permanently discontinue all study treatment and initiate appropriate management in subjects who have been diagnosed with GI perforation or fistula.

Diarrhea: Subjects should be instructed to notify their physician immediately at the first signs of poorly formed or loose stool or an increased frequency of bowel movements.

Guidelines for the evaluation and management of diarrhea are shown in Table 7.4.

Administration of antidiarrheal/antimotility agents is recommended at the first sign of diarrhea as initial management. Some subjects may require concomitant treatment with more than one antidiarrheal agent. When therapy with antidiarrheal agents does not control the diarrhea to tolerable levels, cabozantinib should be temporarily interrupted or dose reduced. When the diarrhea is controlled, retreatment with cabozantinib may be acceptable per investigator decision. In addition, general supportive measures should be implemented such as continuous oral isotonic hydration, correction of fluid and electrolyte abnormalities, small frequent meals, and stopping lactose-containing products, high-fat meals, and alcohol.

Recurrent or prolonged diarrhea can be associated with anal or perianal skin erosions which increase the risk for anal abscesses, fistulas, or proctitis. Good personal hygiene should be emphasized. Regular examinations of the perianal region should be performed whenever diarrhea has occurred during treatment with cabozantinib. Infections of the perianal region should be treated per local guidelines.

Table 7.4: Management of Diarrhea Associated with Cabozantinib

Status	Management
Tolerable Grade 1-2 (duration < 48 h)	
Continue with study treatment and consider dose reductionInitiate treatment with an antidiarrheal agent (e.g., loperamide 4 mg followed by 2 mg after each episode of diarrhea [maximum: 16 mg loperamide per day])Dietary modifications (e.g., small lactose-free meals, bananas, and rice)Intake of isotonic fluids (1-1.5 L/day)Re-assess after 24 hours:
Diarrhea resolving to baseline bowel habits: gradually add solid foods and permanently discontinue or decrease antidiarrheal treatment after 12 h diarrhea-free intervalDiarrhea not resolving: Continue/resume antidiarrheal treatment
Intolerable Grade 2, Grade 2 > 48 h, or ≥ Grade 3	
Interrupt study treatmentAsk subject to attend clinicRule out infection (e.g., stool sample for culture)
Administer antibiotics as needed (e.g., if fever or Grade 3-4 neutropenia persists > 24 h)Administer fluids (1-1.5 L/day orally or IV, as appropriate) for hydration or to correct electrolyte abnormalities

	
• For Grade 3-4 or complicated lower grade diarrhea consider hospitalization and IV hydration• Re-assess after 24 h
○ Diarrhea resolving to baseline bowel habits or Grade \leq 1: consider restarting study treatment at reduced dose○ Diarrhea not resolving: Start and or continue antidiarrheal treatment (e.g., loperamide 4 mg followed by 2 mg after each episode of diarrhea [maximum: 16 mg loperamide per day]). Consider starting second line antidiarrheal or referral to gastroenterologist
--	--

Nausea and vomiting: Antiemetic agents are recommended as clinically appropriate for treatment or prophylaxis of nausea and vomiting, along with supportive care. Dehydration and electrolyte abnormalities may be associated with vomiting and monitoring for and correction of fluid and electrolyte disturbances should be implemented. Antiemetic medications should be assessed for potential drug interactions (refer to Section 6.8.5).

Non-Gastrointestinal Fistula: Complications from radiation therapy especially of the thoracic cavity including mediastinum have been identified as a possible predisposing risk factor for non-GI fistula formation in subjects undergoing treatment with VEGF pathway inhibitors.

Permanently discontinue all study treatment and initiate appropriate management in subjects who have been diagnosed with a non GI fistula.

Hemorrhage: Hemorrhagic events, including serious and sometimes fatal events, have been reported with cabozantinib. Subjects should be monitored for bleeding events with serial complete blood counts and physical examination while on study. The risk of hemorrhage in cabozantinib-treated subjects with brain metastases has not been thoroughly analyzed. Subjects enrolled with treated and stable brain metastases should be monitored with a high index of suspicion if symptoms that could be due to a CNS hemorrhage occur.

All study treatment should be permanently discontinued in subjects with serious and life-threatening bleeding events or recent hemoptysis (≥ 2.5 mL of red blood).

Thromboembolic events: Thromboembolic events are frequent in cancer subjects due to procoagulant changes induced by the malignancy or anticancer therapy. DVT and pulmonary embolism have been observed in clinical studies with cabozantinib, including fatal events. Subjects who develop a pulmonary embolism and/or DVT should have study treatment interrupted until therapeutic anticoagulation is established. Treatment with cabozantinib may be resumed in subjects with pulmonary embolism or DVT if it is determined that the event is uncomplicated and that the subject is deriving clinical benefit from cabozantinib treatment and that the anticoagulation does not place them at a significant risk that outweighs the benefit of resuming treatment per discretion of the investigator and according to individual protocols. Therapeutic doses of LMWH or the direct factor Xa oral inhibitors rivaroxaban, edoxaban, or apixaban are allowed for the management of thrombotic events. Other oral anticoagulants including coumarin agents (e.g., warfarin), platelet inhibitors (e.g., clopidogrel), and chronic use of aspirin above low dose levels for cardio protection per local applicable guidelines are not allowed, until 4 weeks after cabozantinib has been permanently discontinued.

Arterial thrombotic events (e.g., TIA, MI) have been observed in studies with cabozantinib. Subjects should be evaluated for pre-existing risk factors for arterial thrombotic events such as diabetes mellitus, hyperlipidemia, hypertension, coronary artery disease, history of tobacco use, and cardiac and/or thromboembolic events that occurred prior to initiation of study treatment. Further treatment with cabozantinib should be discontinued in subjects who develop an acute MI, cerebral infarction, or any other clinically significant arterial thromboembolic complication.

Hypertension: Table 7.5 provides treatment guidelines for hypertension deemed related to cabozantinib. Blood pressure should be monitored in a constant position visit to visit, either sitting or supine in a relaxed setting. Decisions to reduce or interrupt the dose of study treatment must be based on BP readings taken by a medical professional and must be confirmed with a second measurement at least 5 minutes following the first measurement.

All study treatment should be permanently discontinued in subjects with hypertensive emergency.

Table 7.5: Management of Hypertension Associated with Cabozantinib

Criteria for Dose Modifications	Treatment/Cabozantinib Dose Modification
Subjects NOT receiving optimized anti-hypertensive therapy	
> 150 mm Hg (systolic) ^a and < 160 mm Hg OR > 100 mm Hg (diastolic) and < 110 mm Hg	
 Optimize antihypertensive medications by adding new or additional antihypertensive medications and/or increase dose of existing medications. Reduce cabozantinib treatment by one dose level if optimal antihypertensive therapy (usually to include 3 agents) does not result in BP <150 mm Hg systolic or <100 mm Hg diastolic If subject is symptomatic interrupt cabozantinib treatment
≥ 160 mm Hg (systolic) OR ≥ 110 mm Hg (diastolic)	
 Reduce cabozantinib by one dose level^b or interrupt cabozantinib treatment per investigator discretion Add new or additional anti-hypertensive medications and/or increase dose of existing medications and monitor subject closely for hypotension. If optimized antihypertensive therapy (usually to include 3 agents) does not result in BP < 150 mm Hg systolic or < 100 mm Hg diastolic, cabozantinib treatment should be interrupted Cabozantinib treatment should be dose interrupted if upper limits of systolic BP (≥ 160 mm Hg) are sustained and not adequately manageable or if systolic BP is > 180 mm Hg or diastolic BP > 110 mm Hg, or if subject is symptomatic Re-start cabozantinib treatment at the most tolerable dose and re-escalate only if BP falls to and is sustained at < 150 mm Hg systolic and < 100 mm Hg diastolic
Hypertensive emergency ^c	
 Decide to initiate or adjust antihypertensive. Permanently discontinue all study treatment

^a The investigator may approve treatment at a lower threshold than systolic BP >150 or diastolic BP >100 based on their clinical judgment and assessment of the individual subject.

^b Permitted dose levels are defined by individual protocols and PI discretion.

^c Hypertensive emergency is defined as uncontrolled elevated BP with clinical evidence of progressive or impending end-organ damage (e.g., myocardial infarction/ischemia, intracranial hemorrhage, cerebral ischemia, pulmonary edema, encephalopathy, kidney damage).

Stomatitis and Mucositis: Preventive measures may include a comprehensive oral examination to identify and treat any potential risk for complications before study treatment is initiated. Appropriate correction of local factors should be instituted as indicated, such as modification of ill-fitting dentures and appropriate care of gingivitis. During treatment with cabozantinib, good oral hygiene and standard local treatments such as non-traumatic and non-irritating cleansing, and oral rinses (e.g., with a weak solution of salt and baking soda) should be maintained. Lips should be kept moisturized with lip balm. The use of lipstick, lip-gloss, and Vaseline should be avoided.

Local treatment should be instituted at the earliest onset of symptoms. Obtain bacterial/viral culture if oral infection is suspected and treat infection as clinically indicated.

Skin and Subcutaneous Tissue Disorders: Wound healing and surgery: Cabozantinib has the potential to cause wound healing complications and wound dehiscence, which may even occur long after a wound has been considered healed. Therefore, surgical and traumatic wounds must not only be completely healed prior to starting cabozantinib treatment but must also be monitored for wound dehiscence, wound infection, and other signs of impaired wound healing while the subject is being treated with cabozantinib. If dehiscence occurs, cabozantinib treatment should not be restarted until complete healing has taken place.

Treatment with cabozantinib should be stopped at least 28 days prior to scheduled surgery. The decision to resume treatment with cabozantinib after surgery should be based on clinical judgment of adequate wound healing.

Palmar-plantar erythrodysesthesia syndrome (PPES; also known as hand-foot syndrome), skin rash (including blister, erythematous rash, macular rash, skin exfoliation, dermatitis acneiform, and papular rash), pruritus, dry skin, erythema, pigmentary changes, and alopecia have been reported with cabozantinib. All subjects on study should be advised on prophylactic measures including the use of emollients, removal of calluses, avoidance of exposure of hands and feet to hot water leading to vasodilatation, protection of pressure-sensitive areas of hands and feet, and use of cotton gloves and socks to prevent injury and keep the palms and soles dry.

Early manifestations include tingling, numbness, mild hyperkeratosis, and symmetrical red and swollen areas on the palms and soles. The lateral sides of the fingers or periungual zones may also be affected. Adequate interventions are required to prevent worsening of skin symptoms such as blisters, desquamations, ulcerations, or necrosis of affected areas. Analgesics may be required for pain control.

Aggressive management of symptoms is recommended, including early dermatology referral. Treatment recommendations in response to PPES are summarized in Table 7.6.

Table 7.6: Management of Hand-Foot Syndrome (PPES) Associated with Cabozantinib

CTCAE v.5.0 Grade	Action To Be Taken
Grade 1	Cabozantinib treatment may be continued at the current dose if PPES is clinically insignificant and tolerable. Otherwise, cabozantinib should be reduced to the next lower dose level. ^a Start urea 20% cream twice daily AND clobetasol 0.05% cream once daily. Reassess at least weekly; if PPES worsens at any time or does not improve after 2 weeks, proceed to the intervention guidelines for Grade 2.

Grade 2	Cabozantinib treatment may be continued if PPES is tolerated. Cabozantinib should be dose reduced or interrupted if PPES is intolerable. Continue urea 20% cream twice daily AND high potency steroid cream (e.g., clobetasol 0.05%) once daily and add analgesics (e.g., NSAIDs/gamma-aminobutyric acid agonists) for pain control if needed. Reassess at least weekly; if PPES worsens or affects self-care, proceed to the intervention guidelines for Grade 3.
Grade 3	Interrupt cabozantinib treatment until severity decreases to Grade 1 or 0. Continue treatment of skin reaction with high potency steroid cream (e.g., clobetasol 0.05%) twice daily AND analgesics. Resume study drug at a reduced dose if PPES recovers to Grade ≤ 1 . Permanently discontinue subject from study treatment if PPES does not improve within 6 weeks.

CTCAE, Common Terminology Criteria for Adverse Events; NSAID, non-steroidal anti-inflammatory drug;

PPES, palmar plantar erythrodysesthesia syndrome.

^a Permitted dose levels are defined by individual protocols.

Osteonecrosis: Osteonecrosis has been reported in subjects treated with cabozantinib. Additional risk factors include use of bisphosphonates and denosumab, chemotherapy and anti-angiogenic drugs, use of corticosteroids, local radiotherapy, and dental or orofacial surgery procedures.

Osteonecrosis of the jaw (ONJ) can manifest as jaw pain, osteomyelitis, osteitis, bone erosion, tooth or periodontal infection, toothache, gingival ulceration, or gingival erosion. Persistent pain or slow healing of the mouth or jaw after dental surgery may also be manifestations of osteonecrosis.

Advise subjects regarding oral hygiene practice and to quickly report symptoms to investigator. Caution should be used in subjects receiving bisphosphonates.

Invasive dental procedures should be avoided. In cases where dental procedures are unavoidable, treatment with cabozantinib should be interrupted for at least 4 weeks prior to the procedure and resumed after complete wound healing has occurred. Bone healing may often require a protracted time.

Proteinuria: Proteinuria has been reported with cabozantinib. Proteinuria should be monitored by measuring UPCR. Table 7.7 provides treatment guidelines for proteinuria deemed related to cabozantinib.

All study treatment should be permanently discontinued in subjects who develop nephrotic syndrome (proteinuria > 3.5 grams per day in combination with low blood protein levels, high cholesterol levels, high triglyceride levels, and edema).

Table 7.7: Management of Proteinuria Associated with Cabozantinib

Severity of Proteinuria (UPCR)	Management of Proteinuria
≤ 1 mg/mg (≤ 113.1 mg/mmol)	
 • No change in cabozantinib treatment or monitoring

> 1 and < 3.5 mg/mg (> 113.1 and < 395.9 mg/mmol)	
Consider confirming with a 24-h protein assessment within 7 daysNo change in cabozantinib treatment required if UPCR \leq 2 mg/mg or urine protein \leq 2 g/24 h on 24-h urine collection.Dose reduce or interrupt cabozantinib treatment if UPCR $>$ 2 mg/mg on repeat UPCR testing or urine protein $>$ 2 g/24 h on 24-h urine collection. Continue cabozantinib on a reduced dose if UPCR decreases to $<$ 2 mg/mg. Consider interrupting cabozantinib treatment if UPCR remains $>$ 2 mg/mg despite a dose reduction until UPCR decreases to $<$ 2 mg/mg. Restart cabozantinib treatment at a reduced dose after a dose interruption.Repeat UPCR within 7 days and once per week. If UPCR $<$ 1 mg/mg on 2 consecutive readings, UPCR monitoring can revert to protocol-specific times. (Second reading is confirmatory and can be done within 1 week of first reading.) If UPCR remains $>$ 1 mg/mg and $<$ 2 mg/mg for 1 month or is determined to be stable ($<$ 20% change) for 1 month, check urine protein/creatinine per protocol or as clinically indicated.
\geq 3.5 mg/mg (\geq 395.9 mg/mmol)	
Interrupt cabozantinib treatment pending repeat UPCR within 7 days and/or 24-h urine protein.If \geq 3.5 mg/mg on repeat UPCR, continue to interrupt cabozantinib treatment and check UPCR every 7 days. If UPCR decreases to $<$ 2 mg/mg, restart cabozantinib treatment at a reduced dose and monitoring of urine protein/creatinine should continue weekly until the UPCR decreases to $<$ 1 mg/mg. If UPCR remains $>$ 1 mg/mg and $<$ 2 mg/mg for 1 month or is determined to be stable ($<$ 20% change) for 1 month, check urine protein/creatinine per protocol or as clinically indicated.
Nephrotic syndrome	
Permanently discontinue all study treatment

RCC, renal cell carcinoma; UC, urothelial carcinoma; UPCR, urine protein/creatinine ratio.

Nervous System Disorders: Cabozantinib appears to represent minimal risk of adverse neurological effects based on nonclinical Good Laboratory Practice (GLP)-compliant toxicology studies. Dysphonia, dysgeusia, headache, dizziness, confusional state, convulsion, depression, memory impairment, hypoesthesia, peripheral neuropathy, insomnia, ataxia, and encephalopathy have been observed in clinical studies with cabozantinib. The development of any new or progressive, unexplained neurological symptoms should be assessed for underlying causes.

RPLS has been reported. RPLS should be considered in any subject presenting with seizures, headache, visual disturbances, confusion or altered mental function. All study treatment should be permanently discontinued in subjects with RPLS.

Hepatocellular Toxicity: Investigators should monitor for DILI diligently and report any potential events.

Elevation of aminotransferases (ALT and AST) and bilirubin have been observed during treatment with cabozantinib. It is recommended that subjects with elevations of ALT, AST, and/or bilirubin have more frequent laboratory monitoring of these parameters. If possible,

hepatotoxic concomitant medications should be discontinued in subjects who develop increased values of ALT, AST, or bilirubin, and other potential causes for these increases (e.g., cancer-related infection) should be evaluated. Management guidance for hepatotoxicity related to cabozantinib is provided in Table 7.8.

Table 7.8: Management of Liver Function Laboratory Abnormalities Related to Cabozantinib

Severity of ALT, AST, Total Bilirubin Elevations by CTCAE v.5.0	Treatment Dose Modification
Grade 1	
• Dose adjustment is usually not required.• Consider discontinuing concomitant hepatotoxic medications and add supportive care as indicated.
Grade 2	
• Interrupt study treatment if lasting longer than 1 week and consider more frequent monitoring of ALT, AST, and bilirubin.• Restart study treatment after lab abnormalities have resolved to at least CTCAE Grade ≤ 1 or baseline.
